6. STUDY PROCEDURES

Interventions: For up to seven days, enrolled subjects will either receive 1) one-hour music listening sessions twice daily through noise-cancelling headphones, or 2) one-hour sessions consisting of a silence track twice daily through noise-cancelling headphones.

a. Music Intervention: Twice daily one-hour intervention will be delivered based on our extensive playlist created by our board-certified music therapist consultant and used in our previous studies. The playlist contains relaxing slow tempo instrumental music (60-80 beats/minute). Featured instruments in the playlist include piano, harp, reed, guitar and Native American flute. The mix features classical music and relaxing melodies and does not contain lyrics or spoken words. In addition to the twice daily music intervention sessions, patients will be encouraged to self-initiate listening to slow-tempo music from the study playlist whenever desired as a means to engage in quiet time or listening enjoyment. Our iPad® app will efficiently log all of the 'as desired' music listening sessions by automatically capturing frequency, length, and music selections for both the twice daily music intervention sessions as well as the self-directed listening sessions. Variability in self-directed music listening duration and frequency will be used as a covariate in subsequent analyses.

b. Attention Control: A silence only track will be added to the study iPads® and will be activated in the form of an app similar to the music listening tracking app. Patients randomized to this arm will receive a noise cancellation headphone-applied condition identical to the music intervention experimental treatment; twice daily one hour-sessions. Likewise, patients will have the opportunity to use the silence app with headphones whenever desired. As with the music intervention, the app will track each session's length, frequency, and self-directed headphone application with the silence track.

[figure not shown]

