- **6. Limits of Assumptions:** It is possible that baseline differences between the groups, excessive study dropouts and/or missing data by the interim measurement time point (midway point to targeted enrollment) will limit the value of data analysis. Baseline differences will be evaluated after the first measurement time point and effects on the power to detect differences in the primary outcome will be evaluated and communicated to the PI, safety officer, and NIA. Given the monitoring plans outlined elsewhere in this document, it is exceedingly unlikely that there will be baseline differences between groups of any magnitude to threaten the validity of the study.

Dropout rates higher than 15% would be of concern, so we propose to monitor the dropout rate quarterly. Alert points are set at dropout rates of 15% (low alert), 25% (mid-alert), 35% (high alert) and 45% (extreme alert).

With early alerts to problems, action would be taken to avoid higher-level alerts; if a higher-level alert should arise, more drastic remedial action would be invoked.

The actions taken at each level of alert are given below:

- Mid-level alert = Conference call between study investigators to discuss approaches to minimize further losses to follow-up/dropouts.
- High-level alert = Conference call between investigators and safety officer to determine further alterations of study protocol to complete the study with no further losses.
- Extreme-level alert = In the unlikely event of a 45% dropout rate occurs prior to the six-month measurement time point, study investigators, the safety officer, and the NIA program official would convene on a conference call to discuss the usefulness of continuing the study.

Additional Protocol Materials based on Supplemental Funding

Changes added with protocol amendment 5/22/2023

- 1. Add baseline(prior to/around hospital discharge) and longitudinal outcomes assessment (month 6, month 12) data collection timepoints
 - A. Cognition: Cognition will be measured by 4 objective tests of memory, attention, information processing speed, and executive cognitive function (Auditory Verbal Learning Test [AVLT], Digit Span, and Symbol Digit Modalities Test [SDMT], and Controlled Oral Word Association test [COWA]) using a telephone-based administration format, the Indiana University Telephone-Based Assessment of Neuropsychological Status (IU-TBANS) prior to/around hospital discharge, at 3-months post hospital discharge, 6 months post-hospital discharge.

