Previous research has demonstrated that these tests can be delivered reliably and precisely **in** person or by telephone.⁸⁴

- B. Depression and Anxiety: Research staff will collect PHQ-9 and GAD-7 over the phone or in person prior to/around hospital discharge, at 3 months post-hospital discharge, 6 months post-hospital discharge and 12 months post-hospital discharge.
- 2. Add Blood Sample Collection Time points (month 3, month 6, month 12).

During hospitalization we will collect blood samples prior to first intervention session (up to 10ml in tubes containing anticoagulant), at day 3, and at the end of the intervention period (up to 10 ml in tubes containing anticoagulant). Samples will also be collected at the month 3, month 6 and month 12 post hospital discharge visits (up to 10ml in tubes containing anticoagulant) in the clinic. This will be a total of up to 4 tablespoons of blood collected. The samples will be transported to the CTSI lab, and will be prepared and stored using deidentified labels.

3. Exploratory Aims added (1,2):

Exploratory Aim 1: Test the efficacy of the DDM treatment in slowing the rate of post-ICU cognitive decline in mechanically ventilated patients as compared to attention control. Hypothesis 1a: Patients in the DDM intervention group will have slower cognitive decline compared to the attention control group as measured by the IU-TBANS completed at 6- and 12-months after hospital discharge. Hypothesis 1b: This difference in cognitive trajectories between the DDM intervention group versus the attention control group will be due, in part, to the DDM treatment decreasing the duration and severity of ICU delirium during the index ICU stay.

[figure not shown]

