Exploratory Aim 2: Determine whether the DDM treatment is associated with slower progression of ADRD pathology in older adult ICU survivors as compared to attention control. Hypothesis 2a: Patients in the DDM treatment group will have slower progression in measures of neurodegeneration (lower level of neurofilament light (NfL), phosphorylated tau-181 (p-tau 181), glial fibrillary acidic protein (GFAP), and S100B), AD pathology (higher levels of Aβ42/Aβ40), vascular pathology (lower levels of C-reactive protein (CRP))⁸ and inflammation (lower levels of interleukins (IL)-1, 6, and 8) as measured by blood-based biomarkers collected in the ICU and 3, 6 and 12 months after hospital discharge, compared to those in the attention control group. Hypothesis 2b: These differences in progression of ADRD pathology between the DDM treatment versus control group will be due, in part, to the DDM treatment decreasing the duration and severity of ICU delirium during the index ICU stay.

4. Exploratory Aims Statistical Considerations added (1,2)

Exploratory Aim 1: Mixed effects models will be used with repeated IUTBANS scores (collected at baseline, 6 months and 12 months as the outcome measures), group, time, and a group and time interaction as independent variables while adjusting for stratification variables and other potential baseline covariates found to be significantly different in univariate comparisons. A significant interaction between group and time would indicate differences in changes of cognitive functions over time between the two groups.

Exploratory Aim 2: Changes in the biomarkers will be calculated and used as the dependent variables in ANCOVA models with group as the independent variable and adjusting for stratification variables and baseline covariates that are found to be different among the groups in univariate comparisons. Mixed effects models will be used to explore the association between oxidative stress biomarkers at ICU admission and those collected at 3, 6-, and 12- months post discharge.

5. Revised Figure 3: DDM Trial Flow Chart

6. Revised Table Time-line of Data Collection and Outcomes Assessments

			ata Collection a					
Co	Method of Collection	ne-line of Data Collection and Outcome ICU Phase			Hospital Discharge	Post Hospital Discharge		
		Enrollment	Intervention Phase	Post- intervention phase		3 months	6 months	12 months
Demographics (Age, race, gender, education, Insurance)	EMR	Х						
Clinical Data (lab	EMR	Х						

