Comorbidities (Charlson) ^a	EMR	Х						
Baseline Cognitive function (IQCODE) ^b	Caregiver Interview	Х						
History of depression, Anxiety	EMR	Х						
Diagnoses	EMR	Х			Х			
Severity of Illness ^c (APACHE II, SOFA)	EMR	X (APACHE)						
Functional Status ^d (ADL, IADL)	EMR	Х						
Medications	EMR, patient, caregiver	Х	Daily	Daily	Х	Х	Х	Х
Duration of Mechanical Ventilation, Length of ICU and Hospital stay	EMR				Х			
Mortality	EMR				Х			
Discharge Disposition	EMR				X			
ABCDEF bundle adherence	EMR, Nursing reports	Х	Daily	Daily				
Intervention characteristics	iPad App and Web portal	Х	Х					
Physiologic Parameters (respiratory rate, heart rate, blood pressure)	EMR	Х	4X Daily	Daily				
Delirium, Pain, Anxiety ^f (RASS, CAM- ICU, CAM-ICU-7, CPOT, VAS-A)	Direct Assessment		2X Daily (CAM-ICU, CAM-ICU-7), 4X Daily (RASS, CPOT, VAS-A)	2X Daily				
Cognition (IUTBANS)g	Direct Assessment		, ,		Х	Х	Х	Х
Mood Symptoms ^h (GAD-7, PHQ-9)	Direct Assessment				Х	Х	Х	Х
ICU Experience, Music preference ^{j and}	Direct Assessment				Х			
Specimen collection	Direct Assessment	Х	Х	х		Х	Х	Х
Healthcare Utilization ⁱ	EMR, INPC							Х

°Chronic comorbidities measure through Charlson Comorbidity Index⁸⁹, bIQCODE: Informant Questionnaire on Cognitive Decline in Elderly⁹⁰, Severity of Illness measured through APACHE II⁹¹ and SOFA⁹², Functional Status measured through Katz and Lawton Scales^{93,94}, Analgesic and sedative exposure is defined as aggregate measure of pain and sedation intensity and the drug frequency in a 24 hour period. We will aggregate dose frequency and dosing intensity by each enrollment day. A dose frequency analysis will be used ⁹⁵⁻⁹⁷. FRASS: Richmond-Agitation Sedation Scale⁷⁶, CAM-ICU: Confusion Assessment Method in the ICU⁷⁵, CPOT: Critical Care Pain Observation Tool⁷⁸, VAS-A: Visual Analog Scale-Anxiety⁸¹, gIUTBANS: Indiana University Telephone-Based Assessment of Neuropsychological Status⁸⁴, PHQ-9: Patient Health Questionnaire⁸⁵, GAD-7: Generalized Anxiety Disorder Scale⁸⁷, Captured through Indiana Network for Patient Care (INPC), Intensive Care Experience Questionnaire, Music Preferences Questionnaire. kWe will obtain the Richard-Campbell Sleep Questionnaire around time of extubation (once patient can communicate), at hospital discharge, and at 3-, 6-, and 12-months.

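### Exploratory Aim 1 omits the scheduled 3-month cognition score and judges efficacy only by change from a post-randomization discharge score, so a benefit already present at discharge cannot show in its test

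*Combined protocol and SAP*

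**What the plan says.** All of this is current text in the combined protocol and SAP. Except where noted, it is in the additional materials headed as the amendment of 5/22/2023.

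- **Collection times.** Item 1 reads "Add baseline(prior to/around hospital discharge) and longitudinal outcomes assessment (month 6, month 12) data collection timepoints". Its cognition paragraph gives the times as "prior to/around hospital discharge, at 3-months post hospital discharge, 6 months post-hospital discharge". That sentence stops at 6 months, but the item heading adds month 12. The row "Cognition (IUTBANS)g" in the revised timeline table (item 6) is marked at hospital discharge, 3, 6 and 12 months. It has no mark at enrollment.
- **Hypothesis 1a (item 3).** The claim is "Patients in the DDM intervention group will have slower cognitive decline compared to the attention control group". The visits it names for this are 6 and 12 months only; month 3 is not among them.
- **Model (item 4).** The outcomes are the IU-TBANS scores "collected at baseline, 6 months and 12 months as the outcome measures". The terms are group, time and their interaction, plus stratification variables and any baseline covariates found to differ between groups.
- **Criterion (item 4).** "A significant interaction between group and time would indicate differences in changes of cognitive functions over time between the two groups". No other contrast from this model is named.
- **Timing of treatment (section 6, Study Procedures).** "For up to seven days, enrolled subjects will either receive" music or silence sessions, so the discharge score comes after randomization and after treatment has begun.
- **Use of the 3-month score (Statistical Considerations, Secondary Specific Aim 2).** It is compared between groups by ANCOVA at that single time.

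**The concern.** There are two separate issues. First, a scheduled score is left out of the trajectory model without a stated reason. Exploratory Aim 2, in the same item, does use 3, 6 and 12 months.

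Second, and more important, the starting score is not a pre-treatment measurement. Hypothesis 1b attributes the cognitive effect partly to less delirium during the ICU stay. If that mechanism is right, some of the benefit should already be present at discharge. An interaction measured from discharge takes that part out of the comparison. A null result could then be read as no efficacy. A benefit that wears off could be read as music speeding up decline, even though music patients scored at or above controls at every visit.

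The label also matters outside this aim. Secondary Aim 2 adjusts for unspecified baseline covariates, and item 1 now calls the discharge assessment baseline. The plan does not say that the discharge score will be a covariate there, but nothing in the wording rules it out.

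**Working it through.** **Stated figure.** The plan gives no power for Exploratory Aim 1. The nearest figure is for 3-month cognition (called Aim 3 in the power section): 80% power for 0.5 SD. With 128 evaluable patients, 64 per arm, a two-sample t-test at two-sided α = 0.05 gives 80.1%. The enrollment figure also reproduces: 128 / (1 − 0.20) = 160.

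**Assumptions.** The documents give no IU-TBANS correlation, covariance structure or post-discharge retention, and do not say whether time is linear or categorical. Assumed here: 64 per arm at every visit, compound symmetry with correlation ρ = 0.5–0.7, scores in SD units, time in months from discharge.

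**Interaction with planned times 0, 6, 12.** The mean time is 6, so Sxx = 36 + 0 + 36 = 72. With d(t) the group difference at time t:

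slope difference = Σ(t − 6)·d(t) / 72, with SE = √[2(1 − ρ) / (64 × 72)]

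1. *Constant 0.5 SD benefit from discharge.* The numerator is −6(0.5) + 0(0.5) + 6(0.5) = 0. The slope difference is 0 and the rejection rate is 5%.
2. *0.5 SD at discharge fading linearly to 0 at month 12.* The numerator is −6(0.5) + 0(0.25) + 6(0) = −3, so the slope difference is −3/72 = −0.042 SD per month.
   - ρ = 0.5: SE = 0.0147, |z| = 2.83, power = Φ(2.83 − 1.96) = 81%.
   - ρ = 0.7: SE = 0.0114, |z| = 3.65, power = Φ(3.65 − 1.96) = 95%.

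**Adding month 3.** The mean time becomes 5.25, so Sxx = 27.5625 + 5.0625 + 0.5625 + 45.5625 = 78.75. The variance ratio under compound symmetry is 72 / 78.75 = 0.914, a 9% reduction. It is 0.92–0.94 with random slopes and about 1.00 under AR(1). A test with 80% power would move to about 83%, 83% and 80% respectively. If retention were 85/75/65% at 3/6/12 months (an assumption), the ratios across these structures would run from 0.92 to 0.995.

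**Probability that the interaction is significant** (range for ρ = 0.5–0.7):

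| Benefit in SD at 0/3/6/12 months | Planned, linear time | Planned, categorical time | With month 3, linear | With month 3, categorical |
|---|---|---|---|---|
| 0.5/0.5/0.5/0.5 | 5% | 5% | 5% | 5% |
| 0.5/0.375/0.25/0 | 81–95% (against music) | 72–92% | 84–97% (against music) | 70–91% |
| 0/0.5/0/0 | 5% | 5% | 17–26% (against music) | 84–98% |
| 0/0.5/0.5/0.5 | 81–95% | 84–97% | 66–86% | 84–98% |

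The first two rows show that adding month 3 does not solve the starting-point problem. The last two show that month 3 helps most when time is categorical. With linear time it can even lower power for a benefit that appears by month 3 and persists.

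**The case against.** The strongest reply is that the plan is consistent with its own question. The aim concerns decline after the ICU, for which a start around discharge is natural. Item 1 says openly what it means by baseline, and Hypothesis 1a names only 6 and 12 months. A pre-treatment IU-TBANS is not scheduled, in patients enrolled when expected to be ventilated for at least 48 hours. This stands as a reason for the discharge start. It does not justify reading the interaction as a complete test of efficacy.

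A reader might infer that the trial as a whole would miss an early cognitive benefit. The documents do not support that: Secondary Aim 2 compares the 3-month scores directly and has its own power statement. The Exploratory Aim 1 model also contains a group term, so differences at the modelled visits can be estimated from the same fit. The plan simply does not say that they will be reported.

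A reader might also infer that much data is lost, or that patients seen at 3 months but not later drop out of the analysis. The loss is about 0–9% of slope variance with complete data. In a mixed model such patients still contribute their discharge score. How many there would be cannot be known, because no post-discharge retention is given.

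**Conclusion.** The point holds for the Exploratory Aim 1 test only. Month 3 is scheduled but not modelled, and the score labelled baseline is a post-randomization score. The interaction therefore measures post-discharge change alone. It has 5% rejection for a constant benefit present from discharge. For a 0.5 SD benefit that fades by month 12, it points against music, with 81–95% probability of significance under linear time.

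The 5% result needs no correlation assumption. The other figures depend on 64 per arm, compound symmetry and ρ = 0.5–0.7, and 64 per arm is favorable for month 12 because 128 is the plan's day-7 evaluable number. The benefit patterns are illustrations, not predictions.

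Two remedies look sufficient and are not. Adding month 3 leaves the starting-point problem as it is. So does adjusting for the enrollment IQCODE, a caregiver-reported measure on a different instrument: as a covariate it may add precision, but it cannot restore a level difference to the interaction.

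This is a free improvement of minor severity, because the aim is exploratory.

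**What to change.** In item 4 of the amendment:

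1. Fit the Exploratory Aim 1 mixed model to all four scheduled IU-TBANS scores (discharge, 3, 6 and 12 months), and state how time enters. Categorical time suits visit-specific differences and avoids the loss shown in the last row of the table.
2. Rename the first score discharge (post-randomization), and state that it is not used as a baseline covariate in this model or in Secondary Aim 2.
3. Report model-based group differences with confidence intervals at discharge, 3, 6 and 12 months beside the interaction, and say that the interaction is read only as change after discharge.
4. Optionally, prespecify the enrollment IQCODE as a covariate for precision.
5. Bring the item 1 cognition sentence, which stops at 6 months, into line with the revised table.

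The cost is plan wording. No new visit, test or patient is needed.

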4. INCLUSION/EXCLUSION CRITERIA

DDM Inclusion and Exclusion Criteria					
Inclusion Criteria	Exclusion Criteria				
-Age 50 years or older -English speaking -Admitted to the intensive care unit (medical or surgical) -Expected mechanical ventilator support for ≥48 hours -Consentable through a legally authorized representative -Have access to a telephone	-History of dementing illnesses and other neurodegenerative diseases such as Alzheimer's disease or vascular dementia -Psychiatric illness which is not well controlled -Alcohol withdrawal symptoms/concern for withdrawal -Suspected or confirmed drug intoxication/overdose -Traumatic brain injury, ischemic or hemorrhagic cerebrovascular accident, or undergoing neurosurgery -Uncorrected hearing or vision impairment including legal blindness -Incarcerated at the time of study enrollment -Enrolled in another clinical trial which does not permit co-enrollment				
	-Any medical condition precluding safe use of headphones such as: skin breakdown, burns, facial or skull fractures				

5. ENROLLMENT and RANDOMIZATION

Clinical Settings and Study Population: Patients will be recruited from two Indianapolis Hospital systems: Eskenazi Health and Indiana University Health. Patients will also be recruited from Mayo Clinic Rochester.

Recruitment Targets: Final study sample will comprise 160 mechanically ventilated older adults ≥50 years of age.

Screening and Enrollment: Research staff will review the electronic medical records of ICU patients daily for eligibility. Eligible patients' clinical teams will be approached if necessary to confirm eligibility. Eligible individuals (those who meet inclusion criteria and do not meet any exclusion criteria) will be screened up to twice per day for delirium until approached for the study using the CAM-ICU-7. Once eligibility is confirmed, the research team will approach patients or their legally authorized representatives for consent depending on patients' clinical status. Patients consented through their legally authorized representative will be reconsented once clinically able.

Randomization: Using a computer-generated list of random numbers created by study statistician, participants will be randomized by permuted block with varying block sizes. Randomization will occur after consent in a 1:1 manner and will be stratified based on hospital location.

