3. STATISTICAL CONSIDERATIONS

Statistical Analyses: We will compare baseline patients' demographic characteristics (age, gender, race and levels of education) between the intervention and control group using two sample t-tests for continuous variables and Chi-square tests for categorical variables to determine whether the two groups are balanced in these variables. Variables that are found to be unbalanced will be included as covariates in all models comparing outcomes between the two groups. Intention to treat approach will be used in all analyses.

a. Primary Specific Aim: Delirium/coma free days by day 7 will be compared using analysis of covariance (ANCOVA) model with group (intervention versus control) as the independent variable while adjusting for the baseline patients' demographic variables not balanced between the two groups. For patients discharged before day 7, the days from discharge to day 7 will be counted as delirium/coma free. For patients who died before day 7, 0 delirium/coma free days will be counted from date of death to day 7. We have used the same approach in our previous trials and this approach is able to appropriately handle potential missing data due to discharge or death of patients before day 7.¹⁷

Secondary Specific Aim 1: Mixed effects models will be used to compare delirium severity (CAM-ICU-7), pain (CPOT) and anxiety scores (VAS-A) measured twice daily from randomization to day 7, time of death or discharge. In each of the models, repeated CAM-ICU-7, CPOT or VAS-A scores will be the outcome variable respectively. Group, time, group and time interactions will be included as independent variables while adjusting for potential baseline covariates. Significant group and time interactions will indicate differences in changes of these outcomes between the two groups. Post-hoc analyses will be conducted to determine the earliest times when significant differences between these outcomes can be detected. We will compare various variance covariance structures including autoregressive (AR) and variance components blocked by time of the day (am versus pm) using the likelihood ratio tests to determine the most appropriate covariance structure. We will also examine potential non-linear trajectories of change in these outcomes by including quadratic time in the models and by fitting spline models.

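### Exploratory Aim 2 analyses biomarker change without making each marker's pre-first-session level a fixed covariate, which gives up precision that is nearly free.

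*Combined protocol and SAP*

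**What the plan says.** The 5/22/2023 additions (Additional Protocol Materials, item 4, Exploratory Aim 2) set out the analysis in one sentence. The outcome and model are: "Changes in the biomarkers will be calculated and used as the dependent variables in ANCOVA models with group as the independent variable". The covariates are given as "adjusting for stratification variables and baseline covariates that are found to be different among the groups in univariate comparisons". Under Enrollment and Randomization, allocation "will be stratified based on hospital location", so hospital is the stratification variable. The paragraph on sex as a biological variable adds sex to every analysis.

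The only group comparison of baseline variables listed under Statistical Considerations covers "demographic characteristics (age, gender, race and levels of education) between the intervention and control group". No biomarker is among them.

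On timing, item 2 of the additions says that "we will collect blood samples prior to first intervention session", then "at day 3, and at the end of the intervention period", with further samples at months 3, 6 and 12 after discharge. Hypothesis 2a refers to "blood-based biomarkers collected in the ICU and 3, 6 and 12 months after hospital discharge". The analysis sentence names neither the sample from which change is measured nor the one to which it is measured. The nearest text is a separate model for the "association between oxidative stress biomarkers at ICU admission and those collected at 3, 6-, and 12- months post discharge". Oxidative stress markers are not in the Hypothesis 2a list.

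**The concern.** A change score subtracts the early level with its coefficient fixed at 1. A model that includes the early level as a covariate estimates the coefficient from the data. Where the best coefficient is not 1, the change score carries avoidable noise.

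The plan already collects the early level. Under its covariate rule, that level enters only if the groups happen to differ on it, or never, if the univariate comparisons meant are the demographic ones. Under randomization a 5% screen would admit it in about 5% of trials. What is at stake is precision in an aim that depends on patients who survive and attend clinic for blood sampling months later.

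A smaller matter belongs in the same sentence of the plan. Three in-hospital samples exist, two of them taken after sessions have begun, and the plan does not say which one starts the change.

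**Working it through.** **The plan's own figure.** Exploratory Aim 2 has no sample size or power statement. The trial's 128 and 160 belong to the primary outcome. They reproduce: a two-sided t-test at 0.05 for 0.5 SD needs 64 per arm for 80.1% power, and 128/0.8 = 160. They do not bear on this point.

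**Inputs.** From the documents: change as outcome, the covariate rule, the sampling times and 1:1 allocation. Assumed, because the documents do not give them:
- rho, the correlation between the pre-first-session and follow-up levels
- k, the pre-first-session SD divided by the follow-up SD
- a 5% level for the screen (the Aim 2 text sets no level)
- comparable groups among those with follow-up samples

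**Step 1: variance factors,** with the follow-up SD set to 1.
- Change: 1 + k² − 2·rho·k
- Adjusted for the early level: 1 − rho²
- Ratio: 1 + (k − rho)²/(1 − rho²)

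Example, k = 1 and rho = 0.5: change 1 + 1 − 1 = 1.00; adjusted 1 − 0.25 = 0.75; ratio 1.33.

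**Step 2: the screen.** If the marker's own level is tested at 5% and included only when significant, the excess is multiplied by E[z²; |z| < 1.96] = 0.95 − 2 × 1.96 × φ(1.96) = 0.7209, where φ is the standard normal density. The ratio becomes 1 + 0.7209·(k − rho)²/(1 − rho²).

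**Step 3: results.** Variance relative to always adjusting, given as never screened / screened at 5%:

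| k | rho 0.3 | rho 0.5 | rho 0.7 | rho 0.9 |
|---|---|---|---|---|
| 0.5 | 1.04 / 1.03 | 1.00 / 1.00 | 1.08 / 1.06 | 1.84 / 1.61 |
| 1 | 1.54 / 1.39 | 1.33 / 1.24 | 1.18 / 1.13 | 1.05 / 1.04 |
| 1.5 | 2.58 / 2.14 | 2.33 / 1.96 | 2.25 / 1.90 | 2.89 / 2.37 |

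The loss is nil at k = rho. Where k exceeds 2·rho, the change factor exceeds 1, so change is noisier than ignoring the early sample altogether.

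**Step 4: simulation.** With 64 per arm and 20,000 runs, the unscreened ratios at k = 1 were 1.53, 1.32, 1.16 and 1.04, and at k = 1.5 they were 2.54, 2.29, 2.21 and 2.87, close to the formula. The lowest ratio, at k = rho = 0.5, was 0.993 with 64 per arm and 0.987 with 40 per arm. That is the cost of about 1% for estimating the slope.

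A separate simulation at k = 1 (64 per arm, 8,000 runs, true difference 0.5 SD) compared adjusting only when the early levels differ with always adjusting. Power was 66.8% against 82.3% at rho 0.3, 81.3% against 89.8% at rho 0.5, and 95.3% against 97.2% at rho 0.7. The conditional rule's type I error was 4.0% to 4.8%.

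**Step 5: illustration with fewer patients.** Assume 50 per arm with a follow-up sample, a true difference of 0.5 follow-up SD, and rho 0.5. The standard error is √(2v/50), with v = 0.75 when adjusted and v = 0.75, 1.00 and 1.75 for change at k = 0.5, 1 and 1.5. Power is 0.815 adjusted, against 0.815, 0.697 and 0.465 for unscreened change.

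**The case against.** **ANCOVA could be taken to imply baseline adjustment.** The plan's own usage does not support this. It applies the term to delirium/coma free days, which have no baseline value, and to the 3-month scores without naming an earlier value of the outcome. In Aim 2 the covariates are spelled out and the marker's level is not among them.

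**The start sample is hardly in doubt.** This largely stands. Only one sample precedes treatment, the revised timeline marks a specimen at enrollment, and the revised flow chart cannot be read in this text. The pre-first-session sample is the natural reading. A reader might infer that change is to be taken from day 3 or from the end of intervention, which would subtract any effect already present by then. Nothing in the documents proposes that. The gap is a missing detail.

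**The size is assumed.** This stands too. Neither rho nor k is in the documents, and the loss runs from nothing to more than a doubling of variance. The direction is firm; a material loss for any particular marker is not established.

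**Bias or false positives.** A reader might infer that the change analysis is biased or inflates type I error. Change from a pre-treatment sample is a valid comparison if the groups with follow-up samples are comparable, and the simulated error rates do not exceed 5%. Randomization alone does not guarantee that comparability, because follow-up blood exists only for survivors who attend. Adding the covariate would not by itself remove that limitation.

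**Conclusion.** The point holds as a precision improvement. Each marker's pre-first-session level is in hand but is not a fixed covariate, and under the stated rule it would usually be omitted. Apart from about 1% for slope estimation, the change analysis is never more precise than adjusting for that level. At equal SDs its variance is 1.54 times as large at rho 0.3 and 1.05 times at rho 0.9. It is the same at k = rho, and more than double across that range of rho at k = 1.5 without a screen. A 5% screen on the marker's own level recovers only part of the loss. These figures rest on the assumed rho and k and on comparable groups at follow-up.

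A reader might go on to count how many change scores the text allows. No count is firm, because the end points of change are not fixed and Hypothesis 2a covers ICU samples as well as later ones. The primary outcome is unaffected, and for an exploratory aim this is a change that could be made, not one that must be.

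**What to change.** In the Exploratory Aim 2 sentence of the statistical considerations:
- Include each marker's pre-first-session level as a covariate in every model, with hospital, whatever the univariate comparison shows. Keep sex, as the general rule already requires.
- Name the pre-first-session sample as the start of change.
- State which follow-up occasions are analysed.

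With the early level in the model, analysing change or the follow-up level gives the same group difference, so the outcome may stay expressed as change. The cost is SAP wording and one degree of freedom per model. No sample, visit or patient is added.
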